**Table 1. Specific conditions necessitating corticosteroid treatment and discontinuation of the IFN beta-1a treatment**

Condition
Acute eosinophilic pneumonia (AEP)
Diffuse alveolar hemorrhage from vasculitis
Cryptogenic organizing pneumonia
Acute hypersensitivity pneumonitis (HSP)
Pneumocystis jiroveci pneumonia complicating human immunodeficiency virus (HIV)
Nonspecific interstitial pneumonitis and pneumonitis associated with connective tissue disease

## 2.6 Risk/Benefit Assessment and Summary of Rationale

COVID-19 pandemic is a major health concern with insufficient effective treatment options. IFN beta represents a naturally occurring viral defence, but if deficient, associated with more severe disease outcome (Hadjadj et al. 2020, Zhang et al. 2020). ARDS is a severe condition with a high mortality rate, despite progress in ICU medicine. Currently there is no approved pharmacological therapy available for ARDS. Patients with ARDS are treated with intensive support, which includes various strategies for assisted ventilation. Therefore, IV IFN beta-1a is a plausible treatment option to be investigated for the treatment of hospitalized COVID-19 and prevention of the development of ARDS. This is what the current study aims to achieve.

The previous results of the Phase I/II and Phase III studies in ARDS provided evidence for the beneficial effect of IFN beta-1a if not used together with corticosteroids. The safety profile of IFN beta-1a does not indicate serious adverse events based on one phase I study in healthy volunteers and two phase III studies in subjects with ARDS. Observed finding of neutrophils marginalization only in healthy volunteers (although not in severely ill ARDS patients), warrants investigation of complete blood count and leukocyte differential to monitor blood neutrophil levels in this study also.

Non-clinical data from conventional studies of safety, pharmacology, repeated-dose toxicity and genotoxicity reveal no special hazard for humans treated with IFN beta-1a.

Phase III clinical studies (INTEREST and MR11A8-2) and phase I clinical study (FP1CLI011) in healthy volunteers did not identify any major safety risks for FP-1201-lyo. A decrease in IL-6 IL-8 and IFN-gamma values was observed in patients treated with FP-1201-lyo, a finding that was similar to those found in a placebo group (Ranieri et al. 2020). Fever was the most common AE in phase III studies, and all healthy volunteers in the study FP1CLI011 experienced fever as a response to the treatment. The pyrogenic effect is characteristic for IFN beta-1a as well as for other type I IFNs. In healthy volunteers, the body temperature characteristically reached 38–39°C (axillary) 1-2 hours after the FP-1201-lyo administration, and this elevation persisted for around 2 hours (all treated with antipyretic analgesics). The temperature elevations vary substantially among individuals. IFN beta-1a induced fever responds to antipyretic analgesic drugs, which are recommended to decrease (or prevent) the flu-like symptoms associated with IFN beta-1a administration. Serious adverse reactions possibly related to IFN beta-1a reported more than once in phase III clinical trials, include two cases of increased transaminases, two cases of thrombocytopenia, three cases of hypertension, and two cases of rhabdomyolysis. The available information suggests that the present study's risk/benefit ratio is favourable.

Investigating the effect of IFN beta-1a to prevent ARDS in viral pneumonia (and particularly SARS-CoV-2) is especially intriguing because of the potential beneficial effects of IFN beta-1a in direct viral defense, association of type I IFN deficiency with worse outcomes in COVID-19 (Hadjadj et al 2020, Zhang et al. 2020), and the induction of CD73-mediated preventive effects on endothelial barrier function and pulmonary capillary leak. The current study aims to detect the benefit of IFN beta-1a in clinical outcome measures (WHO 9-point ordinal scale), reduced need of mechanical ventilation, mortality and development of organ failure and ARDS versus the current standard of care for COVID-19. Dexamethasone was chosen as the comparator arm to align with treatment guidelines for hospitalized COVID-19 patients requiring supplemental oxygen. The rationale underlying the current design is provided below. Safety of both treatment arms will be assessed equally.

Study subjects will be randomized in a 1:1 ratio of IFN beta-1a: dexamethasone. According to current NIH COVID-19 treatment guidelines, dexamethasone can be considered for all patients receiving increasing amounts of supplemental oxygen, but remdesivir without dexamethasone is a reasonable

treatment option for patients requiring minimal levels of supplemental oxygen. Remdesivir does not impact study treatment.

In the current study, the target population is mild COVID-19 subjects with a need for low levels of supplemental oxygen. Subjects randomised to IFN beta-1a treatment will not receive dexamethasone while on IFN beta-1a, but will receive it if deterioration occurs, at which point IFN beta-1a will be discontinued. However, not receiving dexamethasone should not subject the study participants to an increased risk for harm for the following reasons:

In the RECOVERY trial (on which the NIH recommendations are largely based), increasing benefit from corticosteroids was associated with increased COVID-19 severity. The greatest benefit was seen in patients receiving invasive mechanical ventilation, somewhat less benefit in patients receiving supplemental oxygen (but not invasively ventilated), and no benefit – with a suggestion of harm - in patients not receiving supplemental oxygen (The RECOVERY Collaborative Group 2020). Unfortunately, the RECOVERY trial data were not sufficiently granular to identify the impact of the dose of oxygen in non-intubated patients, i.e., supplemental oxygen at low flows vs higher flow conventional oxygen vs high flow nasal oxygen vs non-invasive ventilation. Nonetheless, these data suggest a dose-response curve for benefit in relation to the patient's underlying severity of disease, as determined by the application of supplemental oxygen. Given this dose-response, it is uncertain if subjects with low flow supplemental oxygen derive any benefit from dexamethasone.

The rationale to randomise patients (IFN beta-1a or dexamethasone) with hospitalized COVID-19 patients requiring lower flow oxygen supplementation is justified; IFN beta is an anti-viral that should be initiated relatively early for COVID-19 to enhance the dual mechanisms: natural anti-viral effect + protection of alveolar-capillary barrier function (see [Sections 2.2.1](#) and [2.3](#)). Corticosteroids are very effective immunosuppressants, but strong immune-suppression early in the disease course may be detrimental as evidenced by data suggesting worse outcomes with dexamethasone in COVID-19 patients with mild disease, i.e., those hospitalized patients not receiving supplemental oxygen. Study subjects randomised to IFN beta-1a, will not receive dexamethasone at the earliest stage of the disease (while on low flow supplemental oxygen), but importantly, will receive it should their condition deteriorate as evidenced by the need for higher doses of supplemental oxygen (i.e., high flow oxygen at flow rates greater than 10 l/min, use of high flow nasal oxygen, non-invasive ventilation, or invasive ventilation).

### 3 STUDY OBJECTIVES

#### 3.1 Primary Objective

- To demonstrate the safety and tolerability of early IV IFN beta-1a administration in hospitalized patients with COVID-19 infection compared to dexamethasone
- To investigate the efficacy of IV IFN beta-1a to improve clinical status in hospitalized patients with COVID-19 compared to dexamethasone

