## 4 OVERALL DESIGN AND PLAN OF THE STUDY

### 4.1 Overview

This is a multicentre Phase II, double-blind, randomized and controlled, study of the safety and preliminary efficacy of IV IFN beta-1a compared with dexamethasone in adult patients diagnosed with COVID-19 needing hospitalization, but not invasive mechanical ventilation or high flow/presurized supplemental oxygen. The primary endpoint safety and tolerability of IV IFN beta-

1a, and primary efficacy endpoint is WHO ordinal scale for clinical improvement (WHO OSCI) score at D14. Both treatment groups will receive standard care according to current treatment guidelines, except open-label corticosteroids during study days D1-D6 (or other co-medication with potential of interacting with IFN beta-1a; [Section 5.7](#)). If the patient receives (oral or intravenous) glucocorticoids during study days D1-D6, the IMP will be discontinued, and the patient will continue with in all follow-up study assessments.

[figure not shown]
Approximately 140 subjects are planned. Patients with COVID-19 admitted to hospital will undergo screening during which written informed consent will be obtained and eligibility assessed. Not more than 48 hours may elapse between arrival to hospital and administration of the first dose of study drug. An interactive web-response system (IWRS) will be used to randomise the patients using age and gender as stratification parameters.

Following randomization, patients will be treated daily with IFN beta-1a 10 µg or dexamethasone 6 mg as an IV bolus for 6 days and will undergo daily assessments while hospitalized. The main analysis and reporting will use D14 and D28 data. D90 data will be analysed separately. Final follow-up will occur at D90 by phone or through medical records. The overall duration of the study for a patient is therefore 3 months. During the long-term follow-up periods patient care will follow normal hospital procedures, as appropriate. The study will be completed when the last patient completes D90 study assessment. The study design is summarised in [Figure 1](#).

Discontinuation criteria for individual patients and the entire study are described in [Section 4.8.1](#).

The study design incorporates an Independent Data Monitoring Committee (IDMC) that will review ongoing safety (i.e., adverse events [AEs] and serious AEs [SAEs]) and will also make recommendations to the Sponsor as described in the IDMC charter. Details of the IDMC are given in [Section 8.8](#).

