## 7.2 General Considerations

All statistical tests will be two sided and will be performed at the significance level of 0.05, unless otherwise stated.

Continuous data will be summarised by treatment group using descriptive statistics (number, mean, median, standard deviation [SD], minimum and maximum). Categorical data will be summarised by treatment group using frequency tables (frequencies and percentages).

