### 7.4 Determination of Sample Size

140 patients will be randomised 1:1 for active: comparator. Conditional Power re-assessment will be conducted at interim analysis after circa 70 patients have been enrolled and followed up for the primary efficacy endpoint variable. The primary variable is the clinical status at Day 14 using the WHO 9-point scale (0=no detectable infection to 8=death). It will be analysed using ordinal logistic regression model comparing the odds of having better clinical status (smaller number in the 9-point scale) at Day 14 between treatment groups. The sample size is based on an assumption of odds ratio of 0.43 between groups leading to a power of 80% with 70 evaluable patients per group. In the interim analysis the conditional power will be calculated based on the observed result and the sample size will be increased in case the conditional power is in the predefined promising zone. The details of interim analyses will be given in IDMC charter created at the study initiation and in an interim analysis plan which will be finalised before breaking the blind for interim analysis.

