### 7.6.1 Adverse Events

AEs and SAEs will be coded using the current version of Medical Dictionary for Regulatory Activities (MedDRA) and will be classified by system organ classes and preferred terms. In the event that intensity or relationship of an AE to the study drug is missing, a worst-case scenario will prevail (severe in intensity or probably related). Only TEAEs (AEs that occur after the first study drug administration, that were not pre-existing or that increased in intensity) will be included in the summary tables. Counting will be performed for patients and events separately. Patients experiencing the same event more than once will have that event counted once within the corresponding system organ class and with a unique preferred term. All AEs will be included in the data listings. Listings of SAEs, of AEs leading to study drug withdrawal and of AEs leading to death will also be provided.

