The exploratory objectives of this study were to investigate the efficacy of IV IFN beta-1a on clinical outcomes in hospitalized patients with COVID-19 compared to dexamethasone, to measure the pharmacodynamic (PD) effects of IFN beta-1a (MxA and CD73), to measure IFN beta levels during the treatment, to evaluate potential inflammatory markers (PIMs) response to treatment, and to evaluate genetic susceptibility to IFN beta-1a treatment.

4 Design and type of the study

This was a multicentre Phase II, double-blind, randomized and dexamethasone controlled, study of the safety and preliminary efficacy of IV IFN beta-1a compared with dexamethasone in adult patients diagnosed with COVID-19 needing hospitalization, but not invasive mechanical ventilation or high flow/pressurized supplemental oxygen. The primary endpoint safety and tolerability of IV IFN beta-1a, and primary efficacy endpoint is WHO ordinal scale for clinical improvement (WHO

OSCI) score at D14. Both treatment groups received standard care according to current treatment guidelines. If the patient was subjected for systemic (oral or intravenous) glucocorticoids during the study days D1-D6, the IFN IMP is discontinued, and the patient continued in all follow-up study assessments.

The study population consisted of patients that came into the emergency department for a deteriorated condition due to a suspected or already confirmed SARS-CoV2 infection during the previous 7 days. Approximately 140 subjects were planned to be recruited.

Following randomization, patients were treated daily with IFN beta-1a 10 µg or dexamethasone as an IV bolus for 6 days and undergone daily assessments while hospitalized. The main analysis and reporting were meant to use D14, D28 and D90 data. Final follow-up occurred at D90 by phone or through medical records. During the long-term follow-up periods patient care will follow normal hospital procedures, as appropriate.

5 Sample size considerations

140 patients were to be randomised to active and dexamethasone with 1:1 ratio. Conditional power re-assessment was planned to be conducted at interim analysis after 70 patients have been enrolled and followed up for the primary efficacy endpoint variable.

Sample size calculations were performed and documented earlier, see Appendix A.

6 General statistical considerations

No formal statistical hypotheses are set to be analysed due the early termination of the study with only 5 recruited subjects.

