Collected data will be listed and presented descriptively only. Following summary tables will be presented in support to patient listings:

- Study termination and primary reason for discontinuation
- Patient disposition
- Demographic characteristics
- Study drug exposure
- Summary of Treatment-Emergent Adverse Events (TEAEs)
- Deaths

Summary tables regarding adverse events (AEs) will be presented at least by system organ class (SOC), preferred term (PT) and severity including number of patients and events for all TEAEs, severe TEAEs, serious TEAEs, drug-related TEAEs, serious drug-related TEAEs and TEAEs leading to study drug discontinuation.

Based on the data from only 5 individual subjects some of the tables may be left out from the final table package due the sparsity of the table to be meaningful to produce, for example, deaths will not be tabulated if all study participants are alive.

7 Hardware and software

Tables and patient data listings are produced with SAS® 9.4 TS1M6 for Windows (SAS Institute Inc., Cary, NC, USA).

8 References

1. HIBISCUS Study Protocol, version 4.0 (27th September 2021), Faron Pharmaceuticals Ltd.

9 Appendices

- A. HIBISCUS updated sample size calculation, final version (1st April 2021).

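### The primary safety objective is worded as a comparative demonstration, but adverse events get only counts by arm, with no between-arm estimate or interval for SAEs, severe TEAEs or TEAEs that stop study drug

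*Protocol*

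**What the plan says.** Protocol 3.1, like the synopsis, lists as its first primary objective "To demonstrate the safety and tolerability of early IV IFN beta-1a administration in hospitalized patients with COVID-19 infection compared to dexamethasone". The efficacy objective beside it is only to be investigated, and immunogenicity (3.2) only assessed. Protocol 4.1 names safety and tolerability as the primary endpoint, and SAP section 4 repeats this: "The primary endpoint safety and tolerability of IV IFN beta-1a, and primary efficacy endpoint is WHO ordinal scale for clinical improvement".

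The planned analysis is as follows.

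- **Adverse events (Protocol 7.6.1).** TEAEs are tabulated by system organ class and preferred term: "Counting will be performed for patients and events separately". Listings cover SAEs, AEs leading to withdrawal of study drug and fatal AEs. Anti-drug antibodies are counted by group (7.6).
- **Mortality (7.5.2).** Cox hazard ratios with 95% CIs, as secondary efficacy endpoints on the FAS.
- **ARDS, AKI, mechanical ventilation (7.5.3).** Odds ratios with 95% CIs, as exploratory endpoints. The same section compares the arms on transition to open-label corticosteroids.
- **Sample size and hypotheses (7.4, 7.5.1).** Both cover the Day 14 ordinal score only. The basis is an "assumption of odds ratio of 0.43 between groups leading to a power of 80% with 70 evaluable patients per group".
- **Testing (7.2).** "All statistical tests will be two sided and will be performed at the significance level of 0.05, unless otherwise stated". No safety test is specified.

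The SAP was written after termination with five patients dosed. Section 3 restates the objective with the same verb. Section 6 sets no hypotheses and says "Collected data will be listed and presented descriptively only".

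**The concern.** To demonstrate safety against a comparator, a plan needs at least an estimate of the difference and a statement of how large an excess the data leave open. For SAEs, severe TEAEs and TEAEs leading to discontinuation, this plan yields two columns of counts. It has no risk difference, interval, margin or acceptable upper limit, and no statement of what result would meet the objective.

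The reader of the study report would have to judge the first primary objective by comparing percentages by eye. At 70 per arm, similar percentages leave room for excesses that most readers would regard as important, and a table of counts does not show this. An interval would.

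**Working it through.** **1. The plan's own figure.** The only sizing statement is 70 per group for 80% power at an odds ratio of 0.43. Under the proportional-odds (Whitehead) formula, N = 12(z₀.₉₇₅ + z₀.₈₀)² / [(ln OR)² × (1 − Σp̄³)], where p̄ are the mean category probabilities. With ln 0.43 = −0.844, the smallest possible total is 12 × 7.849 / 0.7123 = 132.2. A total of 140 needs 1 − Σp̄³ = 132.2/140 = 0.945. Five equally likely control categories give 138.8, so the figure is attainable. It cannot be confirmed, because the documents give no category distribution (the SAP cites a sample size appendix whose content is not in the text). It concerns efficacy only. There is no safety power, precision or margin figure to reproduce.

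**2. What equal counts would leave open.** Input: n = 70 per arm (Protocol 7.4, "140 patients will be randomised 1:1 for active: comparator"). The observed rates of 10%, 20% and 50% are assumptions. The last is close to the placebo-group SAE rates of 50.7% and 47.7% in Protocol 2.3.4, which come from ARDS trials.

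Wilson limits for each arm: [p + z²/2n ± z√(p(1−p)/n + z²/4n²)] / (1 + z²/n), with z = 1.96.

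Newcombe upper limit for the risk difference: (p₁ − p₂) + √[(U₁ − p₁)² + (p₂ − L₂)²].

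| Observed in each arm | Wilson 95% limits | Upper limit of difference |
|---|---|---|
| 7/70 (10%) | 4.9% to 19.2% | √(0.0923² + 0.0507²) = 10.5 points |
| 14/70 (20%) | 12.3% to 30.8% | √(0.1082² + 0.0770²) = 13.3 points |
| 35/70 (50%) | 38.6% to 61.4% | √(0.1140² + 0.1140²) = 16.1 points |

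The simple Wald half-width 1.96√(2p(1−p)/70) gives 9.9, 13.3 and 16.6 points, so the choice of method hardly matters.

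**3. How sensitive a naive comparison would be.** No safety test is planned, so this step only shows how much a bare comparison of counts can reveal. Power is for a two-sided 0.05 test of two proportions with 70 per arm, at the rates that Protocol 2.3.3 and 2.3.4 quote (IFN beta-1a vs placebo):

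| Contrast | Power |
|---|---|
| SAE 53.5% vs 50.7% | 5% |
| SAE 53.1% vs 47.7% | 9% |
| Drug-related AE 28.5% vs 21.7% | 15% |
| Fever 12.5% vs 7.9% | 14% |
| Anaemia 11.1% vs 7.2% | 12% |
| Day 28 mortality 26% vs 23% | 6% |
| Day 28 mortality 40% vs 21% | 69% |
| Fever 34.7% vs 6.8% | 99% |

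The design would show a very large effect, would often show a 19-point one, and would seldom show differences of 3 to 7 points.

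**4. Objective against analysis.** Deaths are a listed safety criterion (Protocol 4.2.1) and have an interval through 7.5.2, on a population close to the safety set, since FAS and safety set both require at least one dose. The other three outcomes have no interval anywhere in the protocol.

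**The case against.** A reader might infer two stronger things. The documents support neither.

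- **That every harm gets only counts.** This is wrong. Mortality has adjusted hazard ratios with 95% CIs, and ARDS, AKI and ventilation have odds ratios with 95% CIs. These are harms in this population, whatever heading they sit under.
- **That the plan will declare safety from a non-significant difference.** No section says so. Protocol 7.2 sets the level for tests that are performed, 7.5.1 states hypotheses for efficacy only, and 7.6 plans no safety test.

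Further points stand on the other side. Descriptive safety tables are usual in phase II. Protocol 4.3 already speaks of evaluating safety, and Protocol 8.8 gives an independent committee unblinded SAE data at about 20, 40 and 70 subjects. The earlier rates come from ARDS patients against placebo, not low-oxygen COVID-19 patients against dexamethasone. Recruitment ended at five, so an edit to 7.6.1 changes no result, and SAP section 6 already rules out a formal comparative claim.

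All of this limits the point without removing it. Committee review is monitoring and does not define when the objective is met. The existing ratios are not linked to the safety objective. SAEs, severe TEAEs and TEAEs leading to discontinuation still have no between-arm estimate under an objective framed as a comparative demonstration.

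**Conclusion.** The point holds as a mismatch between wording and analysis, and it is minor. The adverse-event part of the first primary objective rests on counts. At the planned 70 per arm, even identical counts would leave an excess of about 10 to 16 percentage points open, depending on an assumed event rate between 10% and 50%. Counts alone therefore cannot support the comparative verb, although a difference as large as the earlier 27.9-point one in fever (34.7 − 6.8) would be evident. The conclusion does not depend on any claim that the sponsor would misread a null result. For the trial as it ended, only the verb in SAP section 3 is still live. The rest concerns the protocol design.

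**What to change.** In Protocol 7.6.1, add for the safety set the risk difference (IFN beta-1a minus dexamethasone) with a two-sided 95% CI, by the Newcombe or Miettinen-Nurminen method, for patients with:

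- any SAE;
- any severe TEAE;
- any TEAE leading to discontinuation of study drug.

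Report the mortality contrast already planned in 7.5.2 beside these. State that the intervals are estimates showing which excess is and is not ruled out, and that a non-significant difference is not evidence of safety. No margin is needed once the claim is one of estimation.

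Change *demonstrate* to *evaluate* in the synopsis, Protocol 3.1 and SAP section 3. A sentence in SAP section 6 saying that five patients support no comparative safety conclusion is optional, since that section already sets no hypotheses and keeps the data descriptive.

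The cost is one extra table from data already collected, a few words of text, and a more modest safety claim. No additional patients or assessments are needed.
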